(1) Protocol assignment adherence	Proportion of eligible patients for whom the protocol assignment (telehealth initiated versus usual care) is followed	Adherence will be 75% or greater
(2) Fidelity: timing of delivery	Whether the telehealth connection is initiated prior to the patients' arrival to the children's hospital	Fidelity will be 75% or greater
(3) Survey response rate	Survey response rates for each survey-derived outcome	Survey response rates will be 75% or greater

Procedures Involved

Randomization: The unit of randomization will be the community hospital, which decreases contamination in comparison to randomization at the patient level (under which each ED would have simultaneous telehealth visits and usual care). We will use constrained randomization to better balance the intervention and control arms with respect to ED-to-children's hospital distance and pediatric transfer volume. Distance will be categorized into less than 21 miles, 21-50 miles, and more than 50 miles. Transfer volume will be categorized into less than 21, 21-60, and more than 60 annual pediatric transfers that arrive as direct admissions to a pediatric ICU or pediatric acute care unit.

Intervention: Per standard procedures, after a children's hospital physician accepts a patient for transfer, the transferring patient is assigned a hospital unit by the bed control nurse. The charge nurse will accept or deny the patient to their unit. Upon accepting a patient to their unit, this charge nurse will determine whether the transferring patient meets trial eligibility criteria and is transferring from an intervention-arm ED site. Upon confirmation that the patient is eligible to receive a nurse-to-family telehealth visit, the charge nurse will call by telephone the community hospital ED and ask the bedside nurse to offer a telehealth visit to the patient's parent(s). If the parents would like to have a nurse-to-family telehealth visit, the ED nurse will give the parent's cell phone number or email address to the children's hospital charge nurse.

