Although we do not anticipate strong cluster effects for the feasibility objective outcomes, we recognize that our confidence intervals will be inflated both by the modest intracluster correlation and by the use of critical values from t-distributions with only 5 or 2 degrees of freedom, depending on whether the objective concerns patients from all 6 sites (objectives 1 and 3) or from just the 3 intervention sites (objective 2). Hence, we anticipate that our actual sample size will perform as effectively as a sample size one half smaller for objectives 1 and 3 and as 60% smaller for objective 2. For feasibility outcomes, an actual sample size of 120 will be sufficient to estimate proportions with error margins (i.e., half-width of 95% CI) of ≤ 12.7 percentage points for the primary feasibility objective (objective 1) and for objective 3, which involve the full sample. For objective 2, we anticipate fidelity testing on an actual sample of size 45, which will result in error margins no greater than 23.0 percentage points. This pilot trial is not powered to determine the relative benefit of telehealth versus usual care, as that important question will be answered in a future efficacy trial. The chosen sample size of 120 patient encounters prioritizes feasibility over power.

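### The margin of at most 12.7 points is not guaranteed for the primary feasibility objective, because pooling six sites from two arms counts the expected arm gap in adherence as between-site variance

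*Combined protocol and SAP*

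**What the plan says.** Table 1 defines objective 1 as one figure across both arms: "Proportion of eligible patients for whom the protocol assignment (telehealth initiated versus usual care) is followed". The success criterion is 75% or more.

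The SAP says confidence intervals will allow for clustering by ED site. It does not mention stratifying by arm. Its last paragraph pairs all six sites with 5 df for objectives 1 and 3, referring to "critical values from t-distributions with only 5 or 2 degrees of freedom". On effective size it says: "our actual sample size will perform as effectively as a sample size one half smaller for objectives 1 and 3 and as 60% smaller" (the last figure belongs to objective 2). It concludes that "an actual sample size of 120 will be sufficient to estimate proportions with error margins" of at most "12.7 percentage points for the primary feasibility objective (objective 1) and for objective 3, which involve the full sample".

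On clustering it offers only a qualitative statement ("Although we do not anticipate strong cluster effects for the feasibility objective outcomes") and calls the intracluster correlation modest. It gives no ICC and no site sizes. For objective 2 it adds that "we anticipate fidelity testing on an actual sample of size 45".

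The Eligibility and Procedures sections describe how adherence arises. In the intervention arm, telehealth is encouraged but neither nurse nor parent is obliged to use it. The charge nurse starts the process only after confirming an intervention-arm site. Control patients transfer with no contact between the charge nurse and the parent.

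**The concern.** A control site follows its assignment by carrying on as usual, whereas an intervention site follows it only if an optional visit is started. The two groups of three sites should therefore differ in adherence by design. An interval built from six supposedly exchangeable sites with 5 df reads that fixed difference as random variation between sites. Its width then says more about the arm gap than about uncertainty in adherence.

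The margin also carries a hidden condition. It holds only for a very small ICC, which the plan does not state, so a reader cannot check it.

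Objective 1 is the primary feasibility objective, and the SAP uses the estimated proportion and its CI to decide whether the objective is met. A pooled rate can also reach 75% with only half the intervention patients having telehealth started (control 100%, intervention 50%, equal arms), which is what a pilot of this intervention needs to see.

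**Working it through.** **Inputs from the SAP:** 120 patients; effective size one half, so 60; 6 sites, 3 of them intervention; 5 df; 95% two-sided. **Assumptions, not in the documents:** 20 patients per site (120/6), hence 60 per arm; control adherence 97-100%; intervention adherence 75%, as 45 of an assumed 60 would suggest. Critical values: z = 1.960; t = 2.571 (5 df), 2.776 (4 df), 4.303 (2 df).

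**1. The plan's figure.** z*sqrt(p(1-p)/n_eff) at p = 0.5: 1.960*sqrt(0.25/60) = 12.65 points. The stated 12.7 reproduces.

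**2. The ICC it allows.** The 5-df value alone multiplies the variance by (2.571/1.960)^2 = 1.720. Halving the sample is a factor of 2, which leaves a design effect of 2/1.720 = 1.163. With 20 per site, ICC = (1.163 - 1)/19 = 0.0086 (0.0090 if 12.7 is used instead of 12.65). This is the limit at p = 0.5, the case an upper bound must cover. At p = 0.75 a 12.7 margin allows an ICC of about 0.030. Unequal sites lower the p = 0.5 limit: to 0.0077 for an illustrative spread of 10 to 30 per site, and to 0.0062 for 5 to 40.

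**3. Margin by ICC, one homogeneous sample.** 2.571*sqrt(p(1-p)*(1 + 19*ICC)/120), in points:

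| ICC | p = 0.5 | p = 0.75 |
|---|---|---|
| 0 | 11.7 | 10.2 |
| 0.01 | 12.8 | 11.1 |
| 0.02 | 13.8 | 11.9 |
| 0.05 | 16.4 | 14.2 |

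**4. Objective 1 with two arms pooled.** For six site proportions, three at pI and three at pC, the expected between-site variance is (6/5)*((pC - pI)/2)^2 plus the mean binomial variance per site. The half-width is 2.571*sqrt(variance/6). With ICC 0:

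- pC = 100%, pI = 75%: the arm gap gives 1.2*0.125^2 = 0.01875. Alone this is 2.571*sqrt(0.01875/6) = 14.4 points. Adding binomial variance 0.5*(0.1875/20) = 0.0047 gives 2.571*sqrt(0.02344/6) = 16.1 points.
- pC = 97%, pI = 75%: 1.2*0.11^2 = 0.01452, plus 0.5*(0.1875 + 0.0291)/20 = 0.0054, gives 14.8 points.
- pC = 100%: 13.3 points at pI = 80%, 12.7 at 81%, 10.5 at 85%, 7.6 at 90%. The margin is met above about 81%.

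With ICC 0.0086 the 75%/100% figure is 16.3.

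**5. Coverage.** In beta-binomial simulation (100,000 runs, 20 per site, ICC 0.0086), the pooled 5-df interval at 75%/100% has a mean half-width of 15.9 points and covers 99.6%. Its half-width exceeds 12.7 in 80% of runs. With control at 97% it covers about 99%.

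**6. Stratified by arm.** If control sites sit at 100%, only the three intervention sites contribute variance: SE = 0.5*sqrt(pI(1 - pI)*DE/60). At pI = 75% and DE = 1, SE = 0.5*sqrt(0.1875/60) = 0.0280. On 2 df this is 4.303*0.0280 = 12.0 points (13.0 at ICC 0.0086), and simulated coverage is about 95%. On 4 df it is 2.776*0.0280 = 7.8 points (8.4 at ICC 0.0086), but coverage is only about 90%, because the control sites supply no variance information.

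**The case against.** The margin is not an arithmetic slip: it follows from the plan's own halving. Nor is a small ICC inconsistent with the plan, which says it expects no strong cluster effects. Both points stand.

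A reader might infer that 12.7 cannot hold for objective 1. The documents do not support that. The failure needs near-complete control adherence, intervention adherence below about 81%, and a between-site variance that ignores arm. No adherence rate is stated for either arm. The SAP's general wording on clustered methods would also permit a stratified analysis, although its 5 df for objective 1 points to a single six-site sample.

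A reader might also infer that the plan itself assumes 75% adherence in the intervention arm. It gives 45 fidelity patients without a denominator or a reason. The balancing of sites on distance and volume does not fix 60 patients per arm, and 45 may be a cautious planning number. The 75% is a reasonable illustration and no more.

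The harm is limited. In these scenarios the pooled interval is too wide, so it does not give false assurance about adherence. The half-width of about 30 points that arises at 50% intervention and 100% control adherence is a stress case, well away from what the 45 patients suggest.

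For objective 3 the figures above 12.7 at ICC 0.02 and 0.05 are for p = 0.5. Near the 75% target the margin tolerates an ICC of about 0.03. That softens the practical concern, but an upper bound has to cover p = 0.5.

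**Conclusion.** Wrong as written: the SAP states a precision that the analysis it describes does not guarantee. At 20 patients per site, control adherence of 97-100% and intervention adherence of 75%, the pooled six-site interval for objective 1 has a half-width of about 15-16 points, not 12.7 or less, and covers about 99%. With control at 100%, the promise is kept once intervention adherence exceeds about 81%. Near-complete control adherence is inferred from the described workflow, and 75% from 45 of an assumed 60; both should be read as assumptions.

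For objective 3 the workflow gives no comparable reason to expect an arm gap. There the bound fails only if the ICC passes about 0.009 at p = 0.5, or about 0.03 at p = 0.75.

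It would go too far to call 12.7 a miscalculation, or to say that allowing for arm must widen the interval. A stratified interval on 2 df is 12.0-13.0 points in the same 75%/100% scenario, close to the stated figure and with about nominal coverage.

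**What to change.** 1. For objective 1, report adherence with a 95% CI separately in each arm (3 sites, 2 df), together with the counts. If every control patient is adherent, a t interval from site proportions has zero width.
2. Form any overall adherence CI stratified by arm, with degrees of freedom matching the sites that actually vary: about 2 if control sites are near 100%. Do not default to 4 df, which would cover only about 90% in that case.
3. State the assumed ICC and site sizes, and restate 12.7 for objectives 1 and 3 as conditional on them. For objective 3, at p = 0.5 and 20 per site, the text could give about 12.8 points at ICC 0.01, 13.8 at 0.02 and 16.4 at 0.05. Recompute objective 1 under the stratified analysis.

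The cost is SAP wording and a stratified variance formula, with no extra data. The downside is that arm-specific intervals on 2 df are wide: at 75% in the intervention arm, 4.303*sqrt(0.1875/60) = 24.1 points even at ICC 0. The stated margin also becomes less favourable.

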Data collection: Data collection for the feasibility objectives and exploratory outcomes will include chart review of the electronic health record and parent surveys. Parent surveys will be distributed to one parent per enrolled patient. Parent respondents will include only English-proficient individuals who were with their child during the ED visit. For children who had more than one parent at their ED bedside, we will let the parents select the single respondent. Eligible parents will receive the family-centered care, experience, and anxiety instruments 0-3 days after the ED encounter. Parent distress will be measured at 30 days from the ED encounter. Surveys not completed within 21 days of distribution will be considered non-response. Participants will receive a \$25 gift card for each survey packet that they return. Parents completing both survey packets will therefore receive a total of \$50 in gift cards.

Data collection for the exploratory outcome change in level of care will use chart review. Electronic health record data will be used to abstract patient demographics (age, race, ethnicity, sex, insurance, California Healthy Places Index) and utilization variables (admitting service, length of stay, disposition). Demographic characteristics of family caregivers (age, race, ethnicity, gender, education, smart phone access, digital literacy score) will be collected in the survey packets.

STATISTICAL ANALYSIS PLAN (SAP)

For feasibility objectives, proportions with 95% CI will be calculated for protocol assignment adherence, fidelity, and survey response rates to determine if each of the feasibility objectives is met. For the exploratory

outcomes, analyses will be descriptive, designed to provide effect size estimates with 95% CI. To account for the cluster randomized design, we will use analysis methods for clustered data when estimating confidence intervals, treating ED sites as clusters.

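### For fidelity (objective 2), the 60% discount and the 23.0-point margin contradict the plan's own t critical value on 2 degrees of freedom, which alone costs about 79% of the sample

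*Combined protocol and SAP*

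**What the plan says.** The Statistical Analysis Plan section promises a 95% confidence interval for each feasibility proportion and states that "we will use analysis methods for clustered data when estimating confidence intervals, treating ED sites as clusters". Its precision paragraph then says that "our confidence intervals will be inflated both by the modest intracluster correlation and by the use of critical values from t-distributions". The degrees of freedom are 5 for objectives 1 and 3 (six sites) and 2 for objective 2 (three intervention sites).

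From these two sources of inflation the SAP infers that the sample will perform as "one half smaller for objectives 1 and 3 and as 60% smaller for objective 2". It gives a margin of at most 12.7 points for objectives 1 and 3 with 120 patients. On the fidelity objective it states: "we anticipate fidelity testing on an actual sample of size 45, which will result in error margins no greater than 23.0 percentage points". Table 1 sets the success criterion: "Fidelity will be 75% or greater".

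**The concern.** The 60% is presented as the joint cost of clustering and the t critical value. With 2 degrees of freedom the critical value is more than twice the normal one, so its cost alone should be well above 60%. If so, the 23.0-point margin is too small and cannot serve as an upper bound.

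It is the plan's only statement of how precisely fidelity will be estimated. The SAP says the intervals will be used to determine whether each feasibility objective is met, and it points to a later efficacy trial. Readers would be misled about how much three sites can show.

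**Working it through.** **Inputs from the SAP:** 95% two-sided interval; n = 45 at 3 sites, 2 df (objective 2); n = 120 at 6 sites, 5 df (objectives 1 and 3); discounts of 60% and 50%. **From Table 1:** 75% threshold. **Not given:** a number for the intracluster correlation (ICC), or patients per site. Where needed I assume equal sites: 15 each for objective 2 (45/3) and 20 each for objectives 1 and 3 (120/6).

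**1. The plan's own figures.** Wald half-width at p = 0.5, z × 0.5/√n_eff:
- Objectives 1 and 3: n_eff = 120 × 0.5 = 60; 1.96 × 0.5/√60 = 12.65 points (printed 12.7).
- Objective 2: n_eff = 45 × 0.4 = 18; 1.96 × 0.5/√18 = 23.1 points (printed 23.0).

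So 23.0 follows from the 60%, apart from rounding. The step to test is the 60%.

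**2. Cost of the t critical value alone.** Loss = 1 − (z/t)², with z = 1.960.

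| df | t(0.975) | (t/z)² | Loss with ICC 0 | Plan's total loss |
|---|---|---|---|---|
| 5 (objectives 1, 3) | 2.571 | 1.720 | 41.9% | 50% |
| 2 (objective 2) | 4.303 | 4.819 | 79.2% | 60% |

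For objective 2, 45/4.819 = 9.3 effective patients.

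**3. What each discount implies for clustering.** The implied design effect is the plan's inflation divided by (t/z)².
- Objectives 1 and 3: 2/1.720 = 1.16, so ICC = 0.16/19 ≈ 0.009. This is coherent with a modest positive ICC.
- Objective 2: 2.5/4.819 = 0.519, so ICC = (0.519 − 1)/14 ≈ −0.034. A negative ICC would narrow the interval, whereas the plan says the ICC widens it.

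**4. Half-width with t on 2 df, n = 45, ICC 0.** Wald form, t × √(p(1 − p)/n):
- p = 0.5: 4.303 × 0.5/√45 = 32.1 points.
- p = 0.75: 4.303 × √(0.1875/45) = 27.8 points. The plan's 18 effective patients give 1.96 × √(0.1875/18) = 20.0.
- Ratio: 32.1/23.1 = 27.8/20.0 = 1.39.

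Other interval forms, same t and n:

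| Form | p = 0.5 | p = 0.75 | Interval at 75% observed |
|---|---|---|---|
| Plan (z, n_eff 18) | 23.1 | 20.0 | 55% to 95% |
| Wald, t(2) | 32.1 | 27.8 | 47% to the 100% ceiling |
| Logit, t(2) | 28.3 | 26.2 | 41% to 93% |
| Wilson-type, t(2) | 27.0 | 24.5 | 43% to 92% |

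**5. With a positive ICC (assumed values, 15 per site).** Design effect 1 + 14 × ICC. At p = 0.5 the Wald half-width is 34.2 points for ICC 0.01, 36.3 for 0.02 and 41.8 for 0.05.

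**6. Planning value versus realised margin.** I simulated 400,000 trials of three sites with 15 patients each, ICC 0, and half-width 4.303 × SD(site proportions)/√3. At p = 0.5 the realised margin averages 28.5 points, exceeds 23.0 in 63% of trials and exceeds 32.1 in 41%. At p = 0.75 it averages 24.6 and exceeds 23.0 in 54%. So 32.1 is a planning value, not a bound.

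**The case against.** The strongest reply concerns weight. Objective 1 is the primary feasibility objective and its margin is sound. The SAP says 120 encounters were chosen with feasibility ahead of power, so nothing was sized on 23.0. Table 1 sets no confidence-limit rule, and the reported interval will come from the data. All of this stands and limits the consequence.

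A second reply is that 23.0 may still be achieved. In the Wald form with t on 2 df and ICC 0, the half-width is 22.9 points at 85% fidelity and 19.2 at 90%. In the simulation, 37% of trials at p = 0.5 and 46% at p = 0.75 come in at 23.0 or less. That is correct, but the plan states a maximum. Its printed figures match p = 0.5, and the maximum already fails at the plan's own 75% threshold.

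Third, the simulation and the ICC values assume equal sites, which is unlikely because the randomization categories run from fewer than 21 to more than 60 annual transfers. With an assumed 25/14/6 split at p = 0.75 and ICC 0, the share of trials above 23.0 is 62% for unweighted site means and 44% for a pooled ratio estimator. Those percentages are therefore illustrative. The 79% does not depend on site size.

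Fourth, the Wald form is inferred from the match to 12.7, since the SAP does not name an interval method, so 32 is one method's figure. The other two forms checked also exceed 23.0.

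Finally, the 60% might come from another critical value: t on 3 df costs 62%, and a 90% interval on 2 df costs 55%. Neither fits the stated 2 df and 95% level.

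**Conclusion.** The concern holds. For objective 2 the stated 60% loss is incompatible with the stated 2 df: the critical value alone costs 79%, leaving 9.3 effective patients rather than 18, and any positive ICC adds to the loss. This needs only the plan's confidence level, degrees of freedom and n.

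The 23.0 points therefore fail as an upper bound. Taking ICC 0 and the Wald form, the planning half-width is 32.1 points at p = 0.5 and 27.8 at p = 0.75, which is 1.39 times the plan's basis. To hold 23.0 at p = 0.5 on those terms would take 0.25 × (4.303/0.23)² = 87.5, that is 88 patients rather than 45.

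The error is confined to the stated precision of a non-primary objective in a pilot. It should be corrected, but it does not affect the validity of the planned analysis.

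**What to change.** In the precision paragraph of the SAP:
- For objective 2, replace the 60% reduction with about 80%: 79% from the t critical value on 2 df alone, and more with any positive ICC.
- Replace the 23.0-point maximum with a planning half-width of about 32 points at 50% fidelity with no clustering, larger with a positive ICC. Describe it as a planning value, not an upper bound.
- The sponsor should recompute the final figure from its own assumed ICC, expected site sizes and interval method, and state all three. The 32 points hold only until that is done.
- Leave the figures for objectives 1 and 3 unchanged.

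The cost is SAP wording only: no added patients, no new decision rule and no change to the analysis. The one drawback is a less favourable stated precision for fidelity.

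### Objective 1 pools adherence over both arms and objective 2 has no written denominator, so the criteria may not show how often telehealth is initiated in time in the intervention arm

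*Combined protocol and SAP*

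**What the plan says.** Table 1 defines the objective 1 indicator as "Proportion of eligible patients for whom the protocol assignment (telehealth initiated versus usual care) is followed", with the criterion "Adherence will be 75% or greater". It sets no threshold by arm. The SAP's precision paragraph calls objective 1 the primary feasibility objective.

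For objective 2, Table 1 gives the indicator as "Whether the telehealth connection is initiated prior to the patients' arrival to the children's hospital" and the criterion as "Fidelity will be 75% or greater". No denominator is written. The SAP says the objectives draw on patients "from all 6 sites (objectives 1 and 3) or from just the 3 intervention sites (objective 2"), and then "we anticipate fidelity testing on an actual sample of size 45". It does not explain the 45 or give an expected number of patients per arm.

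Three other places bear on the point:

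- Under Eligibility, telehealth is encouraged in the intervention arm, but nurses and parents may decline it.
- Under Procedures Involved, the charge nurse starts the telehealth workflow only after confirming that the patient comes from an intervention site. Control families have no contact with the charge nurse before transfer.
- The SAP's opening paragraph says proportions with 95% CIs will determine whether each objective is met. It does not say whether the estimate or a confidence limit decides.

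**The concern.** The main unknown in this pilot is how often the intervention workflow gets started, and started in time. It depends on a charge nurse's call, an ED nurse's offer, a parent's agreement and a suitable phone. Objective 1 averages that unknown with a control-arm proportion expected to be close to 100%, so good control adherence can offset poor uptake. If objective 2 then counts only patients with telehealth initiated, those never started drop out of it as well, and no criterion covers them.

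The pilot is meant to prepare an efficacy trial. If both criteria were met while timely initiation was low, that trial could be planned around a contrast between arms weaker than the pilot appeared to support.

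**Working it through.** **Inputs from the documents.** Total sample 120; objective 2 sample 45; sample-size discounts of one half (objectives 1 and 3) and 60% (objective 2); stated margins 12.7 and 23.0 points; all from the SAP precision paragraph. Thresholds of 75% are from Table 1.

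**Assumptions, not in the documents.** Intervention share of patients *s*, control adherence *c*, and whether the point estimate or a confidence limit decides. The base case is *s* = 0.5, *c* = 100% and a point-estimate rule.

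**1. The plan's own margins.** Half-width = 1.96 × √(0.25 / n_eff).

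- Objectives 1 and 3: n_eff = 120 × 0.5 = 60, giving 12.65 points (stated 12.7).
- Objective 2: n_eff = 45 × 0.4 = 18, giving 23.1 points (stated 23.0, a difference of 0.1).

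The plan's basis is therefore reproduced.

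**2. Intervention-arm initiation at which objective 1 is just met.** Pooled adherence = s·a + (1 − s)·c, where *a* is intervention adherence. Setting it to 0.75 gives a = (0.75 − (1 − s)·c) / s. If fidelity is conditional on initiation and also just reaches 75%, timely initiation over all intervention patients is 0.75 × a.

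| s | c | a | 0.75 × a |
|---|---|---|---|
| 0.5 | 100% | 50% | 37.5% |
| 0.5 | 95% | 55% | 41.3% |
| 0.5 | 90% | 60% | 45.0% |
| 0.5 | 75% | 75% | 56.3% |
| 0.4 | 100% | 37.5% | 28.1% |
| 0.6 | 100% | 58.3% | 43.8% |

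In whole patients, the base case is 60/60 + 30/60 = 90/120 = 75%. The *a* column does not depend on the objective 2 denominator; the last column does.

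**3. Where 45 may come from.** Half of 120 is 60, and 60 × 0.75 = 45. That fits fidelity assessed only in initiated patients at the adherence target. It would also fit 45 intervention patients in all, with 75 controls. The documents do not settle which.

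**4. Timely initiation if fidelity is conditional on initiation (60:60 split, c = 100%).**

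- Boundary case: 30 initiated, 23/30 = 76.7% timely (met), so 23/60 = 38.3%.
- At the plan's 45: 34/45 = 75.6% timely (met), so 34/60 = 56.7%. Pooled adherence is then (60 + 45)/120 = 87.5%.
- Lower 95% limit must reach 75% (Wald, plan's discounts): objective 1 needs about 84.25% pooled, so a = (0.8425 − 0.5)/0.5 = 68.5%. Objective 2 then has n_eff = 0.685 × 60 × 0.4 = 16.4 and needs about 89.7%. The product is 0.685 × 0.897 = 61%.

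**5. Timely initiation if fidelity covers all intervention patients.** Meeting objective 2 would require at least 45/60 = 75%, or 34/45 under a 45:75 split. The compounding in step 4 disappears, and objective 2 would catch what objective 1 misses.

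**6. Margin for intervention-arm adherence.** n_eff = 60 × 0.4 = 24, giving 1.96 × √(0.25/24) = 20.0 points.

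**The case against.** A reader might infer that the plan restricts fidelity to initiated patients, and that feasibility can therefore be declared when about 38% of intervention families get a visit. The documents do not support that as stated, for four reasons.

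- The conditional denominator is inferred from 45 = 0.75 × 60. The reference to patients from the three intervention sites equally allows all of them, and randomizing sites does not guarantee 60 patients per arm.
- The 38% needs an equal split, perfect control adherence, both criteria only just met, a point-estimate rule, and 30 initiated patients where the plan anticipates 45.
- Both indicators count initiation. The parent may not join, so neither 38% nor any other figure here is a rate of completed visits.
- The plan has no combined go/no-go rule under which feasibility would be declared.

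It is also fair to say that control adherence is informative. Charge nurses must classify each patient's site correctly, and telehealth is already a clinical resource for all transfers, so contamination is possible. Separating adherence from timing is a legitimate choice, and where to set a pilot threshold is a judgment.

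These points limit the compounding claim. They do not remove the pooling in objective 1 or the missing denominator in objective 2. Contamination is a reason to report control adherence separately; it does not justify averaging it with uptake.

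**Conclusion.** The concern holds in a limited form. As the primary feasibility criterion, objective 1 can be met with telehealth initiated in about half of eligible intervention patients, given equal arms, complete control adherence and a point-estimate rule; at 90% control adherence the figure is 60%. That follows from pooling, whatever denominator objective 2 uses.

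Whether objective 2 makes up for this cannot be told from the plan. If its denominator is all intervention patients, it does. If it is initiated patients only, which is plausible but unwritten, no criterion measures timely initiation in the whole arm, and meeting both criteria is compatible with roughly 38% (boundary), 57% (the plan's 45) or 61% (lower-limit rule). With equal arms, every scenario examined on that reading falls below 75%. An unequal split moves the boundary figure: 28% if the intervention arm holds 40% of patients, 44% if it holds 60%.

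This is a gap in definition that should be closed before the criteria are applied. It does not invalidate the design.

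**What to change.** Amend the wording of Table 1 and the SAP as follows.

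1. Report adherence by arm, apply the 75% criterion of objective 1 to the intervention arm, and report control-arm adherence as a measure of contamination.
2. State the objective 2 denominator and where 45 comes from.
3. Report, with a cluster-adjusted 95% CI, the proportion of all eligible intervention-arm patients with telehealth initiated before arrival, counting not initiated as failure. Give the rate among initiated patients beside it.

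Item 3 should be reported without its own 75% threshold. Such a threshold would make the adherence criterion redundant, because timely initiation in 75% of the arm implies initiation in at least 75%. With 45 of 60 initiated, it would also be met only if all 45 were timely.

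The cost is a criterion that is harder to meet and an adherence interval resting on about 60 patients in three sites. The margin is about 20 points on the plan's 60% discount, against 12.7 pooled. No new data are needed.
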